- Approximately 10 mL of venous blood will be collected immediately prior to the first study vaccination for baseline serum antibody assays.
- Approximately 10 mL of venous blood will be collected immediately prior to the first study vaccination for baseline clinical safety labs (WBC, Hgb, PLT, ALT, T. Bili, and Cr), and performed by the central (clinical) laboratory. The results from this blood draw will not be available or reviewed prior to study vaccination, and will serve as a safety baseline assessment only.
- Approximately 10 mL of venous blood will be collected prior to study vaccination for future research from subjects who consent to collection of serum for future use either by signing an ICF that includes collection of future use samples as a condition of study participation or by indicating that they can opt in to sample collection for future use if the ICF allows the option to choose that option.
- Subjects will then receive a single dose of study vaccine via IM injection into the deltoid muscle of the preferred arm. The site of injection (right or left arm) and time of administration will be recorded on the appropriate data collection form. Subjects will be observed in the clinic for at least 20 minutes after the first study vaccination. The first study vaccination site will be examined, post-administration reactogenicity assessments will be performed, and any AE/SAEs will be recorded on the appropriate data collection form prior to discharge from the clinic.
- Subjects will be provided with a Memory Aid and other study-related materials to record daily oral temperature, solicited injection site and systemic reactions, any unsolicited AEs, and concomitant medications. Subjects will be encouraged to take their oral temperature around the same time each day. Subjects must not eat or drink anything hot or cold, or smoke within 10 minutes prior to taking oral temperature. Subjects will be instructed on how to use their Memory Aid and how to measure and record AEs prior to discharge from the clinic. Subjects will be instructed to notify the study center if they develop any severe reactions after the first study vaccination. If the site PI or appropriate sub-investigator deems the

reaction severe enough, further instructions will be given to the subject on the proper course of action, including a return to the clinic for immediate evaluation if appropriate.

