3.1.3. Exploratory

Immunogenicity:

- To assess the effects of age, sex, body mass index, and prior receipt of seasonal influenza vaccine(s) on serum HAI and Neut antibody responses following receipt of two doses of a 2017 H7N9 IIV administered IM at different dosages approximately 21 days apart with or without MF59 adjuvant.

- To assess, in at least a subset of samples, the cross-reactivity of serum HAI and Neut antibody responses to antigenically drifted variants of influenza A/H7 viruses following receipt of two doses of a 2017 H7N9 IIV administered IM at different dosages approximately 21 days apart with or without MF59 adjuvant.
- To assess the durability of serum HAI and Neut antibody responses at approximately 180 days following receipt of two doses of 2017 H7N9 IIV administered IM at different dosages approximately 21 days apart with or without MF59 adjuvant.
- To assess the neuraminidase (NA) content of the 2017 H7N9 IIV and determine the serum antibody responses to NA following receipt of 2017 H7N9 IIV. *Note: analysis plans for this objective will be described in an addendum to this SAP once the NA assay has been selected.*

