3.3. Study Definitions and Derived Variables

For individual subjects, fold rise will be calculated as the ratio of: $\frac{\text{post-vaccination titer}}{\text{pre-vaccination titer}}$, where pre-vaccination value is always the result obtained at Day 1, prior to the priming vaccination. Seroconversion for HAI and Neut assays is defined as either a pre-vaccination titer $< 1:10$ and a post-vaccination titer $\geq 1:40$, or a pre-vaccination titer $\geq 1:10$ and a minimum four-fold rise in post-vaccination titer [5].

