8.3.2. Regression Modeling

Logistic and multivariate linear regression will be utilized to test for the effects of the HA antigen dose and the MF59 adjuvant on seroconversion and GMT, respectively, for the PP population. Similar models will be fit for HAI and Neut Antibodies. Separate models will be fit for data from Day 21 post dose 2 and Day 180 post dose 2.

Logistic regression will be fit to examine the relationship of HAI seroconversion at 21 days after the 2nd study vaccination with study arm. If the available titer data meets the required assumptions of normality after log transformation, multiple linear regression will be fit to examine the relationship of log transformed titers at 21 days after the 2nd study vaccination with study arm. Both models will be fit with and without adjustment for the following covariates (*Z*): age category (19-34 years, 35-49 years, 50-64 years), sex (female, male), BMI (<30, ≥ 30), and prior receipt of seasonal influenza vaccine (none in past 2 seasons, at least once in past 2 seasons). Modeling assumptions will be checked using standard diagnostic methods (e.g., using the INFLUENCE option in PROC LOGISTIC or PROC GLM). Parameter estimates and odds ratio estimates for the logistic models will be presented in [Table 43](#), [Table 44](#), [Table 45](#), [Table 46](#), [Table 47](#), [Table 48](#), [Table 49](#), and [Table 50](#). Parameter estimates for the multiple linear regression models will be presented in [Table 51](#), [Table 52](#), [Table 53](#), [Table 54](#), [Table 55](#), [Table 56](#), [Table 57](#), and [Table 58](#).

Model 1A: Logistic Regression (without covariate adjustment):

$$\text{logit}[P(\text{seroconversion})] = \beta_0 + \beta_1 \times \text{Study Arm} + \varepsilon$$

Model 1B: Logistic Regression (with covariate adjustment):

$$\text{logit}[P(\text{seroconversion})] = \beta_0 + \beta_1 \times \text{Study Arm} + \beta_2 \times Z + \varepsilon$$

Model 2A: Multiple Linear Regression (without covariate adjustment):

$$\log(\text{titer}) = \beta_0 + \beta_1 \times \text{Study Arm} + \varepsilon$$

Model 2B: Multiple Linear Regression (with covariate adjustment):

$$\log(\text{titer}) = \beta_0 + \beta_1 \times \text{Study Arm} + \beta_2 \times Z + \varepsilon$$

Subjects missing data for one or more covariates will be excluded from Models 1B and 2B.

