9.1. Demographic and Other Baseline Characteristics

Summaries of age, sex, ethnicity, race, BMI, and prior receipt of seasonal influenza vaccine will be presented by site in [Table 18](#) and [Table 19](#) and by study arm overall in [Table 20](#) and [Table 21](#). Age will be summarized as a continuous variable as well as by strata categories. Ethnicity is categorized as Hispanic or Latino, or not Hispanic and not Latino. In accordance with NIH reporting policy, subjects may self-designate as belonging to more than one race or may refuse to identify a race, the latter reflected in the electronic case report form (eCRF) as “No” to each racial option. BMI will be summarized as a continuous as well as categorical variable, categorized as (<30, ≥30). Self-reported history of prior receipt of seasonal influenza vaccine will be categorized as follows: 2017-2018, 2018-2019, receipt of none, or unknown. Demographic information for individual subjects will be provided in [Listing 6](#).

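### Adjusted Model 2B omits the Day 1 titer, and Models 1B and 2B band age and split BMI at 30; the main loss is in the estimated BMI effect, not in the arm contrasts

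*SAP*

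**What the plan says.** SAP 8.3.2 fits four model types in the PP population, for HAI and Neut and for 21 and 180 days after dose 2. Models 1A and 1B are logistic models for seroconversion; 2A and 2B are linear models for log titer. The section states: "Both models will be fit with and without adjustment for the following covariates". The A versions contain study arm only. The B versions add covariates, beginning with "age category (19-34 years, 35-49 years, 50-64 years), sex (female, male), BMI" (below or at least 30), then prior seasonal vaccination. The shells for Tables 51 and 55 have no row for a Day 1 titer, and no other section adds one. Protocol 10.5.3 says only that available covariates may be considered.

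The data are there:

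- Protocol 6.2 and 6.3: "Approximately 10 mL of venous blood will be collected immediately prior to the first study vaccination for baseline serum antibody assays".
- SAP 3.3, for fold rise and seroconversion: "pre-vaccination value is always the result obtained at Day 1, prior to the priming vaccination".
- SAP 9.1: "BMI will be summarized as a continuous as well as categorical variable"; the same section treats age in both ways.
- SAP 3.1.3 lists as an objective: "To assess the effects of age, sex, body mass index, and prior receipt of seasonal influenza vaccine(s) on serum HAI and Neut antibody responses".

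SAP 8.3 is headed exploratory, but SAP 8.1, the primary immunogenicity analysis, points to these models. SAP 8.3.1 expects almost no antibody at baseline, and SAP 4.5.2 sets undetectable titers to 5.

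**The concern.** A single cut on a measured covariate treats a BMI of 22 and one of 29 as the same and places 29.9 and 30.1 in different classes. If the aim includes estimating how BMI and age relate to response, that discards much of the information collected for the purpose. BMI, with one cut, suffers more than age, with two.

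For log titer, a pre-treatment measurement of the outcome is normally the first covariate to consider. Seroconversion already uses the Day 1 titer through its definition, so that gap is confined to the log-titer models, and within them to 2B, since 2A is the deliberately unadjusted version. At stake are the precision of the covariate effects and a small amount of precision in the arm contrasts.

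A smaller matter in the same section: the youngest band is 19-34 in SAP 8.3.2 and in the age shells, but 18-34 in SAP 6.4 and 8.3.1, and eligibility starts at 18. Read literally, an 18-year-old has no age category in the adjusted models.

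**Working it through.** **The plan's own figures.** The documents give no SD, baseline correlation or detectable GMT ratio for the log-titer models, so there is nothing of theirs to reproduce for this point. The nearest figures are Protocol Table 10 (detectable differences, N = 100 per arm), which recomputes to 0.197, 0.193, 0.182, 0.163, 0.134 and 0.090 and matches when rounded up, and Table 11, which also matches. Neither depends on covariate adjustment. All results below rest on stated assumptions.

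**1. BMI split at 30.** For a normal covariate, the share of linear information kept is φ(z)² / [p(1 − p)], with z = (30 − mean)/SD and p = P(BMI ≥ 30).

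- Mean 27, SD 5: z = 0.60, φ = 0.333, p = 0.274; 0.111/0.199 = 0.56.
- Mean 28, SD 6: z = 0.33, φ = 0.377, p = 0.369; 0.142/0.233 = 0.61.

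With the planned analysable total of 3 × 100 + 50 = 350 (Protocol 10.2), this is like having about 195 to 214 subjects for the BMI question.

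**2. Three age bands.** Assume ages uniform from 18 to just under 65. Total variance = 47²/12 = 184. The bands are 17, 15 and 15 years wide, so within-band variance = (17³ + 15³ + 15³)/(12 × 47) = 20.7. Share kept = 1 − 20.7/184 = 0.89.

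**3. Effect of categorising on the arm contrasts.** If a covariate correlates r with the log titer and categorising keeps a share k, the SE is inflated by √[(1 − k r²)/(1 − r²)] − 1, each covariate taken alone.

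| r | BMI (k = 0.60) | Age (k = 0.88) |
|---|---|---|
| 0.1 | 0.2% | 0.06% |
| 0.2 | 0.8% | 0.25% |
| 0.3 | 2.0% | 0.6% |

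**4. Adding log Day 1 titer to 2B.** SE reduction = 1 − √(1 − r²). To obtain r, assume a fraction f has a Day 1 titer of 10, 20 or 40 with equal probability and the rest are at 5. Let the post-vaccination log titer carry over the baseline with slope b, plus residual SD 1.2 on the natural log scale. Then r² = b²V/(b²V + 1.44), where V = (ln 2)² × [14f/3 − (2f)²].

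| f | V | b = 0.3 | b = 0.6 | b = 1.0 |
|---|---|---|---|---|
| 0 | 0 | 0 | 0 | 0 |
| 2% | 0.044 | 0.1% | 0.5% | 1.5% |
| 5% | 0.107 | 0.3% | 1.3% | 3.5% |
| 10% | 0.205 | 0.6% | 2.5% | 6% |

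As a GMT ratio detectable with 80% power for 100 v 50, with an assumed total SD of 1.2: exp[2.80 × 1.2 × √(1/100 + 1/50)] = 1.79 without the term, 1.77 if r = 0.2 and 1.74 if r = 0.3.

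**The case against.** The case for leaving the plan alone is substantial.

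- **The Day 1 titer should hardly vary.** Protocol 5.1.2 excludes prior H7 vaccination or infection and relevant bird exposure, and undetectable values all become 5. If nobody is detectable, the term is collinear with the intercept and cannot be fitted. This stands; the term is only insurance against the expectation failing for one of the assays.
- **Randomisation.** A reader might infer that omitting the baseline biases the Day 43 GMT contrast. The documents do not support that: allocation is random, little baseline variation is expected, and Tables 23-26 display Day 1 GMTs by arm, so an imbalance would be visible.
- **The BMI figure.** A reader might also take a loss of about 40% of information as a loss of power for dose or adjuvant. It concerns the BMI slope only; section 8.3.2 gives the models' purpose as testing dose and adjuvant, and step 3 bounds the effect there.
- **Model 2A.** Adding the Day 1 titer to it would remove the planned comparison with and without adjustment. This stands.
- **Categories match the endpoint.** The exploratory endpoint is worded as stratified summaries, and SAP 6.4 fixes the categories and disclaims power for subgroups. That justifies categories in Tables 27-42. It does not require them in the regression.
- **Linearity.** Continuous terms assume it, and the only diagnostic named, the INFLUENCE option, looks for influential observations and does not test functional form. This stands, so a check must be added.
- **Losing subjects.** It is tempting to say that none would be lost because a pre-vaccination result is required. SAP 6.3.2 requires HAI or Neut, so a subject could lack a valid Day 1 result for one assay.

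**Conclusion.** The point holds as a minor efficiency matter. The clearest loss is in the BMI effect: 56-61% of the linear information kept, assuming normal BMI with mean 27-28 and SD 5-6. Age loses about 11%, assuming uniform ages. The cost to the arm contrasts is about 2% of SE or less for covariate correlations up to 0.3. The Day 1 term is worth nothing if all subjects are below 1:10. With up to 10% detectable it is worth a few percent of SE, reaching about 6% only at the steepest carry-over slope assumed.

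None of this puts a primary summary in doubt, contradicts the protocol or alters a sample-size figure. The plan would be acceptable unchanged, but it would describe the BMI effect less well than its data allow.

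**What to change.** In SAP 8.3.2, before unblinding:

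1. Leave Model 2A as written.
2. Add log Day 1 titer, same assay and strain, to Model 2B, and state that it is dropped if it is constant.
3. Enter age and BMI as continuous terms in Models 1B and 2B, and name a linearity check, for example a quadratic or spline term reported alongside.
4. Keep the categories for Tables 27-42, and correct the 19-34 label there. Continuous age removes the 18-year-old problem from the models.

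The cost is SAP wording, changed model statements and edits to the shells for Tables 47-50 and 55-58. No new data are needed. The downsides are a linearity assumption and possibly a few subjects missing from one assay's Model 2B; their number should be reported. If unblinding has already happened, run this as a labelled supplementary analysis.

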8.3.3. Analysis of Heterologous Strain

HAI and Neut antibody responses against antigenically drifted variants of influenza A/H7 viruses including A/Shanghai/2/2013 and A/Guangdong/17SF003/2016xPR8 will be summarized for the Per-Protocol population as described in Section 8 and presented in

Table 59, Table 60, Table 61, Table 62, Figure 12, Figure 13, Figure 14, Figure 15, Figure 16, Figure 17, Figure 18, and Figure 19. A scatter plot of the correlation between HAI and Neut antibody responses for each of the drifted strains will be presented in Figure 20, Figure 21, Figure 22, and Figure 23. A scatter plot of the correlation between response to the vaccine strain and each heterologous strain will be presented in Figure 24 and Figure 25. No formal hypothesis testing or modeling for the exploratory analysis of heterologous strains is planned.

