3.2.3 Exploratory

Immunogenicity:

- To assess the effects of age, sex, body mass index, and prior receipt of seasonal influenza vaccine(s) on serum HAI and Neut antibody responses following receipt of two doses of a 2017 H7N9 IIV administered IM at different dosages approximately 21 days apart with or without MF59[®] adjuvant.
- To assess, in at least a subset of samples, the cross-reactivity of serum HAI and Neut antibody responses to antigenically drifted variants of influenza A/H7 viruses following receipt of two doses of a 2017 H7N9 IIV administered IM at different dosages approximately 21 days apart with or without MF59[®] adjuvant.
- To assess the durability of serum HAI and Neut antibody responses at approximately 180 days following receipt of two doses of 2017 H7N9 IIV administered IM at different dosages approximately 21 days apart with or without MF59[®] adjuvant.
- To assess the NA content of the 2017 H7N9 IIV and determine the serum antibody responses to NA following receipt of 2017 H7N9 IIV.

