Further, a determination of the NA content of the 2017 H7N9 IIV is planned if an assay becomes available and may be used to correlate the N9 NA elicited antibody responses to the NA content of the 2017 H7N9 IIV. Detectable NA antibody responses and GMTs will be summarized and evaluated for a dose response. If the NA content is available, NA antibody responses will be stratified by NA content, and statistical modeling may be used to examine the relationship of NA response with NA vaccine content, HA antigen dosage, and adjuvant.

At least a subset of samples will also be tested for cross-reactive serum HAI and Neut antibody responses to antigenically drifted variants of influenza A/H7 viruses. Strain-specific results will be summarized using descriptive statistics as described above, correlations with 2017 H7N9 responses, and association with study vaccine dose and adjuvant.

Further immunogenicity testing and/or analyses may be carried out in the future based upon subjects' prior receipt of non-seasonal influenza vaccines, including type (inactivated or live attenuated), what subtype (e.g. A/H3, A/H5, A/H9) and approximate date of vaccination.

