8. IMMUNOGENICITY EVALUATION

Analysis of all immune responses will be conducted using the PP population. In addition, primary endpoint analyses will be conducted with the mITT population. Immune responses in terms of strain-specific A/H7N9 HAI and Neut antibody titers will be summarized by study arm at each time point. Descriptive summary statistics will be provided for all assays and time points including number of subjects with non-missing results, percentage of subjects with titers $\geq 1:40$, percentage of subjects achieving seroconversion, and GMTs along with corresponding 95% CI. Exact confidence intervals will be presented for proportional endpoints. Summaries of primary and secondary immunogenicity endpoints are presented in [Table 23](#), [Table 24](#), [Table 25](#), and [Table 26](#).

Reverse cumulative distribution (RCD) curves will be presented for post-vaccination HAI and Neut antibody titers. Plots for each assay will be generated with 4 panels (8 days post vaccination 1, 21 days post vaccination 1, 8 days post vaccination 2, 21 days post vaccination 2, and 180 days post vaccination 2), and separate curves within each panel for each study arm, as shown in [Figure 2](#), [Figure 3](#), [Figure 4](#), and [Figure 5](#).

Figures depicting the HAI and Neut GMT over time will also be presented as shown in [Figure 6](#), [Figure 7](#), [Figure 8](#), and [Figure 9](#).

The spearman correlation between HAI and Neut antibody titers will be calculated at each time point over all groups. The correlation will be depicted in scatter plots as [Figure 10](#) and [Figure 11](#).

Individual HAI and Neut assay results will be provided in [Listing 8](#) and [Listing 9](#).

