12. SUMMARY OF CHANGES IN THE CONDUCT OF THE STUDY OR PLANNED ANALYSES

This SAP does not include any changes from the analyses described in the protocol.

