Table 58: Multiple Linear Regression Model to Evaluate the Relationship of HA Antigen Dose and MF59 Adjuvant with Log-Adjusted Neut Titer at 180 Days Post Second Study Vaccination, Adjusted for Baseline Covariates, Per-Protocol Population

Table 59: Summaries of Hemagglutination Inhibition Antibody Against A/Shanghai/2/2013 (H7N9) by Study Day and Study Arm, Per-Protocol Population*

Time Point	Study Arm 1 3.75 mcg A/H7N9 + MF59 (N=X)	Study Arm 2 7.5 mcg A/H7N9 + MF59 (N=X)	Study Arm 3 15 mcg A/H7N9 + MF59 (N=X)	Study Arm 4 15 mcg A/H7N9 (N=X)
Day 1 (Pre Vaccination 1)				
n	x	x	x	x
GMT (95% CI)	xxx.x (xxx.x,xxx.x)	xxx.x (xxx.x,xxx.x)	xxx.x (xxx.x,xxx.x)	xxx.x (xxx.x,xxx.x)
Titer ≥ 1:40 - % (95% CI ^a)	xx (xx, xx)	xx (xx, xx)	xx (xx, xx)	xx (xx, xx)
Day 21 Post Vaccination 2				
n	x	x	x	x
GMT (95% CI)	xxx.x (xxx.x,xxx.x)	xxx.x (xxx.x,xxx.x)	xxx.x (xxx.x,xxx.x)	xxx.x (xxx.x,xxx.x)
Seroconversion - % (95% CI ^a)	xx (xx, xx)	xx (xx, xx)	xx (xx, xx)	xx (xx, xx)
Titer ≥ 1:40 - % (95% CI ^a)	xx (xx, xx)	xx (xx, xx)	xx (xx, xx)	xx (xx, xx)
Day 180 Post Vaccination 2				
n	x	x	x	x
GMT (95% CI)	xxx.x (xxx.x,xxx.x) xxx.x (xxx.x,xxx.x)	xxx.x (xxx.x,xxx.x) xxx.x (xxx.x,xxx.x)	xxx.x (xxx.x,xxx.x) xxx.x (xxx.x,xxx.x)	xxx.x (xxx.x,xxx.x) xxx.x (xxx.x,xxx.x)
Seroconversion - % (95% CI ^a)	xx (xx, xx)	xx (xx, xx)	xx (xx, xx)	xx (xx, xx)
Titer ≥ 1:40 - % (95% CI ^a)	xx (xx, xx)	xx (xx, xx)	xx (xx, xx)	xx (xx, xx)
N = Number of subjects in the Per-Protocol Population; n = number of subjects with available results; GMT = Geometric Mean Titer; CI = Confidence Interval ^a 95% CIs calculated using Clopper-Pearson exact methods.				

Tables with similar format:

Table 60: Summaries of Hemagglutination Inhibition Antibody Against A/Guangdong/17SF003/2016 (H7N9) by Study Day and Study Arm, Per-Protocol Population*

Table 61: Summaries of Neutralizing Antibody Against A/Shanghai/2/2013 (H7N9) by Study Day and Study Arm, Per-Protocol Population*

Table 62: Summaries of Neutralizing Antibody Against A/Guangdong/17SF003/2016 (H7N9) by Study Day and Study Arm, Per-Protocol Population*

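### The protocol promises the association of drifted-strain responses with vaccine dose and adjuvant, but the SAP plans no between-arm estimate for it and does not record the omission

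*SAP*

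**What the plan says.** Protocol 10.5.3 on the drifted A/H7 variants: "Strain-specific results will be summarized using descriptive statistics as described above, correlations with 2017 H7N9 responses, and association with study vaccine dose and adjuvant". That is three items, the last being association with dose and adjuvant.

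SAP 8.3.3 says drifted-strain HAI and Neut responses "will be summarized for the Per-Protocol population as described in Section 8 and presented in" Tables 59 to 62 and a set of figures. It adds scatter plots of HAI against Neut and of vaccine strain against drifted strain, and closes: "No formal hypothesis testing or modeling for the exploratory analysis of heterologous strains is planned".

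The Table 59 shell (SAP Appendix 1), which Tables 60 to 62 follow, has four arm columns. Each holds n, GMT, seroconversion and titer ≥1:40, with that arm's own interval. For proportions these are one-sample intervals; SAP 8 says "Exact confidence intervals will be presented for proportional endpoints".

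For the vaccine strain the SAP does more. Section 8.3.2 says "Logistic and multivariate linear regression will be utilized to test for the effects of the HA antigen dose and the MF59 adjuvant"; the outcomes modelled are seroconversion and GMT, with shells in Tables 43 to 58. None of those tables is for a drifted strain.

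SAP 12: "This SAP does not include any changes from the analyses described in the protocol".

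**The concern.** The protocol names association with dose and adjuvant as an item separate from the descriptive statistics, and the SAP plans no quantity that measures it. Because SAP 12 says nothing has changed, a reader of the SAP alone would not know that an announced analysis has been left out.

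Tables 59 to 62 carry the topline mark, and SAP 6.2.1 says topline results may go to the sponsor for planning further trials and to the lead investigator for publication. Readers will compare arms from these tables, and the only comparison on offer is to set separate per-arm intervals side by side. That is less sensitive than an interval for the difference itself.

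**Working it through.** **Setting the passages side by side**

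| Protocol 10.5.3 item | Where the SAP delivers it |
|---|---|
| Descriptive statistics | Tables 59–62; reverse cumulative distribution and GMT figures by arm |
| Correlation with vaccine-strain response | Scatter plots of vaccine strain against each drifted strain |
| Association with dose and adjuvant | No difference, GMT ratio, odds ratio or model in text or shells |

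**Inputs for the size of the loss**
- Analysed n: 100 per adjuvanted arm and 50 unadjuvanted (Protocol 10.2). These are the sizes assumed for the power calculations.
- Unadjuvanted responder rate: 0.10 (Protocol 10.2, Table 11), an assumption for the adjuvant comparison in HAI response, not for drifted strains.
- Adjuvanted responder rate for a drifted strain: given in neither document. I assume 0.30 and vary it.
- Interval for a difference: Farrington-Manning (SAP Table 7, footnote).

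**Formulas**
- Exact per-arm interval: lower limit = Beta quantile at 0.025 with parameters (x, n − x + 1); upper limit = Beta quantile at 0.975 with parameters (x + 1, n − x).
- Score interval for the difference: all d with |p1 − p2 − d| / √[p̃1(1 − p̃1)/n1 + p̃2(1 − p̃2)/n2] ≤ 1.96, where p̃1 and p̃2 are the maximum-likelihood rates under p1 − p2 = d.

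**Reproducing the plan's own figure.** With 100 against 50, unadjuvanted 0.10 and adjuvanted 0.50 / 0.60 / 0.70 / 0.80 / 0.90, the score lower bounds are 0.256 / 0.356 / 0.458 / 0.563 / 0.672. The stated values are 0.26 / 0.36 / 0.46 / 0.56 / 0.67, so all five match.

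**Adjuvant and dose illustrations**

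| Responders | Exact interval, first arm | Exact interval, second arm | Overlap? | Difference | Score 95% interval |
|---|---|---|---|---|---|
| 23/100 v 5/50 | 15.2–32.5% | 3.3–21.8% | yes | 0.13 | −0.003 to 0.242 |
| 24/100 v 5/50 | 16.0–33.6% | 3.3–21.8% | yes | 0.14 | 0.007 to 0.253 |
| 30/100 v 5/50 | 21.2–40.0% | 3.3–21.8% | yes | 0.20 | 0.063 to 0.316 |
| 31/100 v 5/50 | 22.1–41.0% | 3.3–21.8% | no | 0.21 | 0.073 to 0.327 |
| 50/100 v 5/50 | 39.8–60.2% | 3.3–21.8% | no | 0.40 | 0.256 to 0.518 |
| 40/100 v 25/100 (two adjuvanted doses) | 30.3–50.3% | 16.9–34.7% | yes | 0.15 | 0.020 to 0.276 |

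Against 5/50, the band in which the separate intervals overlap although the interval for the difference excludes zero runs from 24 to 30 responders of 100.

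**Effect of assaying a subset.** The protocol promises at least a subset of samples and gives no size; SAP 4.1 mentions no subset. Keeping rates of 30% and 10% with assumed subsets: 18/60 v 3/30 gives a score interval of 0.017 to 0.349; 12/40 v 2/20 gives −0.032 to 0.381.

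**The case against.** The strongest reply is that the protocol asks only for results to be summarized. Its drifted-strain sentence names no model, test or contrast, whereas the same section does name modelling for the vaccine-strain response and for the NA response. Each arm is one dose and adjuvant combination, so by-arm tables could be read as the association. On that reading SAP 12 is not wrong. Part of this stands: the protocol does not require a regression, and an informal by-arm comparison is available. It does not dispose of the point, because the protocol lists association separately from descriptive statistics. If per-arm summaries met it, the third item would add nothing.

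A reader might also infer that the cross-reactivity objective goes unanswered, or that showing whether MF59 or dose broadens the response is a stated goal of the trial. The documents do not support either. The exploratory objective is "To assess, in at least a subset of samples, the cross-reactivity of serum HAI and Neut antibody responses to antigenically drifted variants", and Protocol 2.2.1 asks whether drifted variants are recognized. The endpoints are seroconversion, titer ≥40 and GMT, and Tables 59 to 62 report all three. The commitment on dose and adjuvant sits in Protocol 10.5.3 alone.

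Three further objections stand. No passage says arms will be judged by overlap. The 30/100 example is the last count that overlaps, its rate is assumed, and the protocol's own adjuvant scenarios start at 0.50 against 0.10, where the intervals are clearly apart. And individual titers are to be listed by strain, so a contrast could be computed later; but it would then not be prespecified.

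**Conclusion.** The point holds as a mismatch between documents. Protocol 10.5.3 promises an association with dose and adjuvant for drifted strains, the SAP plans no between-arm estimate of it, and SAP 12 is therefore inaccurate in declaring no change. It does not show that the SAP omits a model the protocol mandates.

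The practical loss is limited to moderate effects: in the illustration, adjuvanted rates of about 24% to 30% against 10%, at 100 and 50 analysed. Differences of the size the protocol tabulates for the adjuvant would be plain from the per-arm intervals. All of this rests on assumed drifted-strain rates and on most samples being assayed; in a subset, even the direct contrast may be too imprecise to settle the question. The analysis is exploratory, in a trial that tests no formal null hypothesis. I rate this as a cheap improvement.

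**What to change.** Add to SAP 8.3.3, with matching rows or columns in Tables 59 to 62:

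*For each drifted strain and each assay at Day 43 and Day 202, differences in the proportions with seroconversion and with titer ≥1:40 (Farrington-Manning score 95% CI) and GMT ratios (95% CI) will be presented for 15 mcg + MF59 versus 15 mcg unadjuvanted and for each pair of adjuvanted dose arms. These estimates are exploratory, are shown without p-values and are not adjusted for multiplicity.*

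The existing sentence on no formal testing or modelling can stay, since these are estimates. With the addition, SAP 12 becomes accurate on this item. If the sponsor prefers not to add them, SAP 12 should record the omission and give the reason.

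Extending Models 1A and 2A to the drifted strains is the less suitable route. The shells use the unadjuvanted arm as reference, so they print no direct contrast between adjuvanted doses. Sixteen models (2 model types × 2 strains × 2 assays × 2 visits) with three arm coefficients each would add 48 unadjusted p-values. The logistic fits may fail by separation if few or no unadjuvanted subjects respond; a score interval for a difference remains computable.

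The programming cost is small. The reporting cost is more unadjusted intervals: 4 contrasts × 2 strains × 2 assays × 2 visits = 32 per endpoint, or 96 over the three endpoints. Dropping one of the two responder endpoints would bring this to 64. The exploratory label must appear on the tables.
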